7.4.4 Surgical Technique

Surgery should occur between 8 and 12 weeks from the completion of neoadjuvant therapy.

Patients will be positioned in lithotomy. The use of ureteral stents will be at the discretion of the treating surgeon. Open and minimally invasive techniques are allowed. If preservation of the anal sphincter muscles is planned, a standard laparotomy will be undertaken. An assessment of the liver, peritoneum, pelvic organs (uterus/ovaries) should be performed. The objective of the operation is a curative

procedure with full total mesentery excision (TME) of the rectum. It will be expected that all attempts to perform a high ligation of the IMA will occur and that the nodes within this portion of the mesentery will be carefully examined. The plane between the fascia propria of the rectum and the presacral fascia will be entered in the midline posteriorly. Every attempt will be made to identify the hypogastric nerves along the pelvic side wall and the findings will be recorded as injured or preserved (See Appendix VI). It is expected that all tumors located in the mid and lower rectum will be removed with a complete TME. All attempts will be made to achieve at least a 3-cm margin on the mesorectum and a 1-cm mucosal margin. If the margin is in question, additional margin should be taken. A frozen section may be performed at the discretion of the treating surgeon. The surgeon will record their assessment of the TME as either complete, nearly complete, or incomplete recording difficulty encountered. It will be at the discretion of the surgeon to perform either a straight end-to-end or side-to-end anastomosis with or without a colonic pouch or coloplasty. Evaluation of the anastomosis will be performed from the abdominal side, i.e., tension-free anastomosis and from the perineal side, i.e., complete ring of the anastomosis and negative air test. All patients undergoing a resection with re-anastomosis will have a diverting loop ileostomy performed. If an APR is performed, the perineum will be removed in an oncological fashion with preservation of the radial margin either at the start of the procedure or at the end of the procedure. The perineum will be closed in a method which is at the discretion of the treating surgeon and the patient will be given a permanent stoma.

Abdominal or perineal drainage will be left to the discretion of the surgeon.

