7.4.6 Follow-Up Evaluation

Patient will be considered for stoma closure 2 to 3 months after surgery or following additional chemotherapy. Prior to stoma closure, patient will have anastomosis evaluation by either standard contrast radiography direct in the rectum and or by rectal exam with sigmoidoscopy. Any abnormal finding will be recorded and may delay stoma closure.

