9. STUDY CALENDAR

Evaluation	Baseline ¹	RADIATION TREATMENT ⁷	Pre-Op ⁸	SURGERY ⁹	Post-Op ¹⁰	CHEMOTHERAPY ¹²	Post Surgical Follow-Up ¹³				
							1Y	2 Y	3Y	4Y	5Y
Informed Consent	X										
H&P	X		X		X		X	X	X	X	X
Performance Status	X		X		X		X	X	X	X	X
Pregnancy Test ²	X										
Concomitant Medications ³	X						X	X	X	X	X
Endoscopic Ultrasound ⁴	X										
Marker Placement ⁵	X										
Research Biopsy ⁵ (optional)	X										
FDG-PET/CT	X		X								
Pelvic MRI	X		X								
CT C/A/P							X	X	X	X	X
CBC w/ Diff, CMP	X		X		X		X	X	X	X	X
CEA	X		X		X		X	X	X	X	X
Testosterone ⁶	X		X					X	X	X	X
Biomarkers (optional, lead site only)	X		X		X			X	X	X	X
TME Evaluation							X ¹¹				
Toxicity Evaluation	X		X		X			X	X	X	X
QOL Surveys ¹⁴	X		X		X			X	X	X	X

1 Must be conducted within 6 weeks of RT initiation

2 Required for premenopausal women who have not been surgically sterilized within 1 month of RT initiation. All women of child-bearing potential must have negative pregnancy test (urine or serum).

3 Specifically: phosphodiesterase inhibitors, bi- and tri-mix injections, testosterone therapy, vaginal estrogen cream, and hormone replacement therapy

4 Must be conducted within 3 months of RT initiation

5 Must be conducted within 3 weeks of RT initiation; biopsy should include tumor and normal tissue sample (see Section 10.4.4)

6 Total and free testosterone level for male participants only

7 Patients will be monitored for toxicity weekly during RT

8 Within 4-8 weeks pre-surgery

9 Patients will undergo surgery 8-12 weeks from RT completion

10 Within 4-12 weeks post-surgery

11 Documentation must be complete within 1 week post-surgery

12 Adjuvant chemotherapy is standard and will not be monitored/tracked by the Principal Investigator or the study team

13 Annual follow-up appointments will be based on the date of surgery and have a tolerance window of +/- 30 days

14 See 9.1 for quality of life survey calendar

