14.5 Analysis of Secondary Endpoints

Secondary endpoints of this phase II trial include toxicity, quality of life, locoregional control/distant metastasis, overall survival, and correlative analyses of biomarkers and functional imaging changes.

The acute and chronic toxicity and adverse events will be summarized in frequency tables by type and grade for each arm and will be compared between arms using Fisher's exact tests.

Quality of life will be assessed via EORTC QLQ-C30 (v3.0) questionnaires as mentioned above. Scoring will be based on procedures outlined by the EORTC. For our study population of rectal cancer patients, the analysis will be focused on general and colorectal model regarding urinary/bowel toxicity, sphincter function, and sexual dysfunction. For each module, summary statistics of the scores will be reported at baseline and each follow-up time. After confirming that there are no baseline differences in quality of life across the two treatment arms using independent samples t-test, changes in quality of life scores from pre- to post-treatment will be computed, and the difference between these change scores will be evaluated by paired-sample t-tests. We will compare the quality of life scores at each endpoint as well as the differences between the two arms using two-sample t-test. Given the plurality of comparisons, p-values <0.01 will be considered statistically significant. In addition, mixed effect models will be used for assessing the quality of life change over time and comparing the two treatment arms. For instance, mixed effects models will be used to assess changes in QOL over time first in all study patients and then to compare the effects of the two treatment arms on change in QOL over time. Need for sexual aids will be compared in a descriptive fashion between the two cohorts.

Overall survival, distant metastases free survival, progression free survival, and local recurrence will be measured from the date of randomization to the date of death due to any causes. Patients last known to be alive are censored at date of last contact. Kaplan-Meier curves will be used to characterize overall survival in each arm and log rank test will be used for the comparison.

The analysis of correlative endpoints of imaging and biomarkers will be exploratory.

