52. Did you have a dry vagina during intercourse?	1	2	3	4
53. Did you have pain during intercourse?	1	2	3	4

54. Do you have a stoma (colostomy bag)?**No**

(Please circle No or Yes)

Yes**Please answer questions 55 to 61****Please skip questions 55 to 61
and answer questions 62 to 68****During the past week:**

	Not at All	A Little	Quite a Bit	Very Much
--	---------------	-------------	----------------	--------------

Only for patients WITHOUT a stoma (colostomy bag):

55. Did you have frequent bowel movements during the day?	1	2	3	4
56. Did you have frequent bowel movements during the night?	1	2	3	4
57. Did you feel the urge to move your bowels without actually producing any stools?	1	2	3	4
58. Have you had any unintentional release of stools?	1	2	3	4
59. Have you had blood with your stools?	1	2	3	4
60. Have you had difficulty in moving your bowels?	1	2	3	4
61. Have your bowel movements been painful?	1	2	3	4

Only for patients WITH a stoma (colostomy bag):

62. Were you afraid that other people would be able to hear your stoma?	1	2	3	4
63. Were you afraid that other people would be able to smell your stools?	1	2	3	4
64. Were you worried about possible leakage from the stoma bag?	1	2	3	4
65. Did you have problems with caring for your stoma?	1	2	3	4
66. Was your skin around the stoma irritated?	1	2	3	4
67. Did you feel embarrassed because of your stoma?	1	2	3	4
68. Did you feel less complete because of your stoma?	1	2	3	4

Treatment-Related Stress

A. Individual items assessing treatment-related stress and impact on daily life.

1. In the last month, how many days of work have you missed because of your cancer treatment?
[0 days; 1-2 days; 3-4 days; 4-6 days; a week or more; not applicable because wasn't working]
2. Overall, how much has your cancer treatment interfered with your daily life?
[0=Not at all; 1=A little bit; 2=Somewhat; 3=Much; 4= Very much]
3. Overall, how much has your cancer treatment caused you stress (e.g., hassles)?
[0=Not at all; 1=A little bit; 2=Somewhat; 3=Much; 4= Very much]
4. In the last month, how much has your cancer treatment interfered with your ability to do your work (including work at home)?
[0=Not at all; 1=A little bit; 2=Somewhat; 3=Much; 4= Very much]
5. In the last month, how much has your cancer treatment interfered with your ability to participate in social activities (e.g., go to church; spend time with friends or family)?
[0=Not at all; 1=A little bit; 2=Somewhat; 3=Much; 4= Very much]

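### The between-arm test of the CR38 bowel-movement and continence items is near-empty at the Post-Op form, and from year 1 it rests on a stoma-free subset that treatment is expected to change

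*Combined protocol and SAP*

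**What the plan says.** Section 14.5 states that "the analysis will be focused on general and colorectal model regarding urinary/bowel toxicity, sphincter function, and sexual dysfunction". It plans two-sample t-tests ("We will compare the quality of life scores at each endpoint as well as the differences between the two arms using two-sample t-test"), adds mixed models over time, and sets the threshold with "p-values <0.01 will be considered statistically significant". On scoring it says only "Scoring will be based on procedures outlined by the EORTC". It gives no rule for stoma status and no evaluable set for items that depend on it.

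Section 9.1 schedules the QLQ-CR38 at Baseline, Pre-Op, Post-Op and years 1 to 5. In Appendix VI (Quality of Life Assessments), item 54 asks whether the patient has a stoma. Items 55-61, on stool frequency, urgency, leakage, blood, difficulty and pain, are headed "Only for patients WITHOUT a stoma (colostomy bag". Patients with a stoma skip them and answer items 62-68.

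On surgery, Section 7.4.4 says "All patients undergoing a resection with re-anastomosis will have a diverting loop ileostomy performed", and Section 11.7 gives APR patients a permanent colostomy. Section 7.4.6 says "Patient will be considered for stoma closure 2 to 3 months after surgery or following additional chemotherapy". Section 7.4.7 places adjuvant chemotherapy from about 6-10 weeks after surgery, for 12 two-week cycles, at the treating physician's discretion. The Post-Op visit is timed in footnote 10 of Section 9: "Within 4-12 weeks post-surgery".

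**The concern.** In the forms printed in the protocol, items 55-61 are the only ones that measure continence and bowel-movement function. Section 10.3.3 hypothesises that Endo-HDR preserves anorectal function in the long term, so these items carry a named claim.

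Three things follow if the plan is run as written. First, the Post-Op t-test of these items would use only the few patients whose stoma was closed early, and the same scores would enter the mixed model. Second, item 54 explains a stoma as a colostomy bag. A patient with a temporary ileostomy might answer no and go on to rate a diverted bowel. Third, from year 1 the respondents are those with a preserved sphincter and a closed stoma. Section 3.3.1 says likely APR candidates are enrolled, and Sections 1 and 4.2 anticipate better sphincter preservation with Endo-HDR. The subset is thus defined after randomisation by something the treatment is meant to alter, and a difference in its mean score is not a randomised comparison of function.

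**Working it through.** The documents give no power, sample size or evaluable number for quality of life, so there is no stated figure to reproduce on this point.

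**Inputs from the documents.** Post-Op form at weeks 4-12 (Section 9). Closure at 2-3 months, or after chemotherapy (7.4.6). Chemotherapy starts at weeks 6-10 and lasts 12 x 2 = 24 weeks (7.4.7). Arms of 92 and 46, with less than 5% drop-out (14.2.1). QOL threshold 0.01 (14.5), taken as two-sided because sidedness is not stated.

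**Step 1: timing.** One month is 365.25/12/7 = 4.35 weeks, so 2-3 months is weeks 8.70-13.04. Chemotherapy ends at weeks 30-34 (6 + 24 to 10 + 24). No closure is due on either route before week 8.70, which covers (8.70 - 4)/(12 - 4) = 59% of the Post-Op window. That is a share of calendar time, not of patients.

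**Step 2: share still diverted at the form.** Assume that the form date is uniform over weeks 4-12 and the early closure date uniform over weeks 8.70-13.04. The chance of closure before the form is (12 - 8.70)^2 / (2 x 8 x 4.35) = 0.157.

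| Diverted patients who wait for chemotherapy to end | Stoma still present at the Post-Op form |
|---|---|
| None | 84% |
| Half | 92% |
| All | 100% |

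**Step 3: valid Post-Op respondents.** Assume sphincter preservation of 60-90% and 5% drop-out. If nobody waits, about 16% are closed:
- Endo-HDR: 92 x 0.95 x (0.60 to 0.90) x 0.16 = 8 to 13 patients.
- Control: 46 x 0.95 x (0.60 to 0.90) x 0.16 = 4 to 6 patients.

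If everyone waits, both numbers are 0.

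**Step 4: year 1.** The annual window is 52.2 weeks plus or minus 30 days, or weeks 47.9-56.5. That lies after both closure routes, so the items can be answered, but only by patients who are stoma-free.

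**Step 5: size of the later selection.** The documents give no preservation rates, so these are assumptions. With preservation of 90% v 80%, and the extra preserved Endo-HDR patients scoring 20-30 points worse on a 0-100 scale, the Endo-HDR mean moves by 10/90 x 20 = 2.2 to 10/90 x 30 = 3.3 points with no true effect on function.

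The evaluable numbers are 92 x 0.90 = 82.8 and 46 x 0.80 = 36.8. With an assumed SD of 20-30, the standard error is SD x sqrt(1/82.8 + 1/36.8) = 3.96 to 5.94. The chance of a significant result against Endo-HDR is Phi(-2.576 + shift/SE):
- smallest case, 2.2 points and SD 30: Phi(-2.576 + 0.374) = 1.4%;
- largest case, 3.3 points and SD 20: Phi(-2.576 + 0.841) = 4.1%.

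The nominal chance in that direction is 0.5%.

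**Step 6: a second model.** Suppose the most favourable fraction s of patients is preserved in each arm, and that favourability correlates with later function at r = 0.3-0.7. The bias in SD units is r x [phi(z1)/s1 - phi(z0)/s0], where each z is the normal quantile at s.
- 85% v 70%: r x (0.274 - 0.497), a bias of 0.07-0.16 SD against Endo-HDR; two-sided type I error 0.014-0.034.
- 90% v 60%: r x (0.195 - 0.644), a bias of 0.13-0.31 SD; type I error 0.026-0.126.

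**The case against.** The strongest reply is that this touches part of one instrument. The QLQ-C30 constipation and diarrhea items (16-17) and CR38 items 34-38 are answered by everyone, and bowel toxicity is also graded under CTCAE. Baseline and Pre-Op forms precede surgery. The planned pre- to post-treatment change could be read as Baseline to Pre-Op, which the surgical stoma does not affect. All of that stands, and it limits the point to items 55-61 from the Post-Op form onward. CRF 21 is scheduled at every visit but its items are not printed, so whether it covers bowel function cannot be judged.

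A reader might infer that the Post-Op comparison is wholly empty. It need not be: 7.4.6 allows closure at 2-3 months, chemotherapy is discretionary, and up to about 16% of diverted patients could already be closed. A reader might also infer that ileostomy patients will misanswer item 54. The question does use the word stoma, and 7.4.2 provides for efforts to have a stomatherapist see patients beforehand. Misreading is a risk, not an established fault.

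It can also be said that the plan already copes: the form has a skip rule, EORTC scoring is specified, the procedure performed is recorded, and sphincter preservation is a secondary objective. This stands only in part. Setting skipped scales to missing leaves the Post-Op test near-empty and does not remove the later selection. Nor does a mixed model, because continence in a patient with a stoma is undefined rather than missing at random. Section 14.5 gives no analysis for sphincter preservation. The CRFs are not in the documents, so stoma type and closure date may already be collected.

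**Conclusion.** The point holds for CR38 items 55-61. At the Post-Op form the planned between-arm test is near-empty and limited to early closures: 84-100% of diverted patients still have the stoma under uniform timing, leaving at most about 8-13 v 4-6 valid respondents under the assumed preservation rates. The timing follows from the protocol's own windows; the percentages rest on the uniform assumption.

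From year 1 the comparison is conditional on being stoma-free, and the trial expects that condition to differ by arm. The direction of concern is against Endo-HDR, but the size is not known. It is tempting to conclude that a real benefit would show up as harm. The documents do not support that: they give no preservation or APR rate, and under an assumed 90% v 80% the chance of a significant false harm is 1.4-4.1% against a nominal 0.5%. The larger biases need gaps such as 90% v 60%.

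This concerns a secondary endpoint of a phase II trial and leaves the primary pCR analysis untouched. It should be corrected because it changes what can be concluded about sphincter function.

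**What to change.** In Section 14.5:

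1. Omit the between-arm test of CR38 items 55-61 at the Post-Op form, and exclude those Post-Op scores from the mixed model.
2. Record stoma status, type and closure date at each QOL form, if the CRF does not already do so. Use that record, not item 54 alone, to decide which items are scored.
3. From year 1, label the comparison of items 55-61 as conditional on being stoma-free. Report beside it the proportion alive and stoma-free by randomised arm, among all randomised patients. Restricting to forms completed after closure would not by itself remove the selection.
4. If a composite that includes continence is wanted, pre-specify and justify its cutoff. The documents offer no basis for one.

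The cost is a few sentences of analysis text and at most two or three CRF fields taken from the surgical record, with no change to care. The downside is that no continence result is claimed at the Post-Op visit.

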1. HYPOTHESIS

Pathologic complete response (pCR) is associated with improved survival and lower risk for distant metastases. Neoadjuvant Endo-HDR will increase pCR rates compared to concurrent chemoradiation (RT + Capecitabine). We expect similar locoregional control, decreased treatment time (1 week as opposed to 6 weeks), improved sphincter preservation rates, and lower acute and chronic toxicity.

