Although these are promising results supporting the use of Endo-HDR, a theoretical concern of using this treatment strategy to treat only the primary site and adjacent mesorectal nodes is the potential for increased pelvic nodal recurrence without elective treatment with external beam radiotherapy (24). Standard NCRT covers the internal iliac, perirectal lymph nodes, mesorectum, and primary tumor (25). Current radiation portals are derived largely from Gunderson and Sosin's detailed study of the pattern of

recurrence after bluntly dissected rectal cancers. However, modern surgical series in patients treated without external beam radiation have shown that the majority of pelvic failures occur locally in the anastomosis and presacral tumor bed and that the incidence of extramesorectal pelvic nodal failure is low both in overall incidence as well as an isolated source of failure (4, 26-28). Wiig, reporting on 100 cases of local recurrence after TME, concluded that all recurrences were within reach of the examining finger and at the tumor bed (26). In the same series, there was only one case of nodal recurrence in the lateral pelvic wall. In the Dutch TME referenced above, the rate of extramesorectal pelvic nodal failure was 1.6% in the TME alone arm versus 1.3% who received preoperative radiation therapy. Moreover, preoperative treatment of extramesorectal nodes with chemoradiation may not improve outcomes. In the MERCURY study, MRI-based assessment of tumor regression and circumferential margin were prognostic for survival after neoadjuvant chemoradiation (29). Importantly, the presence of MRI detected extramesorectal lymphadenopathy did negatively impact disease-free survival; however, the use of neoadjuvant treatment did not alter the negative outcomes of iliac node positivity (29).

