4.2 Secondary Objectives

- Test whether clinical response based on functional imaging (PET, MRI) pre/post radiation (Endo-HDR vs. CRT) predicts for pathologic complete response.
- Utilize preoperative imaging response rates and clinical exam to determine whether Endo-HDR results in improved sphincter preservation rates when compared to CRT.
- Determine whether tumor (VEGF/EGFR status) and blood predict for pathologic response following neoadjuvant Endo-HDR vs. CRT.
- Compare acute and long-term toxicity as well as quality of life for both Endo-HDR and CRT.
- Compare locoregional control, distant metastasis and overall survival for both Endo-HDR and CRT.

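### Section 14.5 times local recurrence although the objective is locoregional control, and neither term is defined, so it is open whether a pelvic nodal failure counts

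*Combined protocol and SAP*

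**What the plan says.** Three places name locoregional control:

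- Section 1 (Hypothesis): "We expect similar locoregional control".
- Section 4.2 (Secondary Objectives): "Compare locoregional control, distant metastasis and overall survival for both Endo-HDR and CRT".
- Section 14.5, opening sentence: "Secondary endpoints of this phase II trial include toxicity, quality of life, locoregional control/distant metastasis, overall survival".

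The later paragraph of Section 14.5 that sets out the time-to-event outcomes uses a different term. Its list is "Overall survival, distant metastases free survival, progression free survival, and local recurrence will be measured from the date of randomization", and the sentence closes with every listed outcome running to death: "local recurrence will be measured from the date of randomization to the date of death due to any causes". Kaplan-Meier curves and a log rank test are then described for overall survival only.

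The documents define neither local recurrence nor locoregional control. They do not say whether a failure in iliac, lateral pelvic or inguinal nodes is an event for either.

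Section 3.1 (Rationale) discusses pelvic nodal recurrence as a theoretical concern of treating only the primary site and adjacent mesorectal nodes. It then gives figures from a cited randomized trial of short-course radiotherapy before TME: "the rate of extramesorectal pelvic nodal failure was 1.6% in the TME alone arm versus 1.3% who received preoperative radiation therapy". The study calendar in Section 9 schedules CT of chest, abdomen and pelvis at each annual visit from year 1 to year 5.

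**The concern.** The outcome that is timed is not the outcome in the objective, and the gap between the two terms falls where the treatments differ. In the control arm, Section 7.3.1.2 puts the internal iliac region inside the elective target volume. In the Endo-HDR arm, Section 7.2.7 defines the target as the gross tumor plus intramesorectal deposits visible on MRI. Section 3.1 itself distinguishes failure at the anastomosis or presacral tumor bed from extramesorectal pelvic nodal failure.

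An analyst who follows the later sentence of Section 14.5 and reads *local* narrowly would leave out isolated pelvic nodal failures. If Endo-HDR did produce more of them, they would be missing from the control endpoint, and the hypothesis of similar control would be assessed without the component most relevant to it. Two sites could also code the same event differently.

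**Working it through.** **Is there a figure to reproduce?** The plan states no expected rate, power or precision for locoregional control or local recurrence. The arm sizes of 92 and 46 come from Section 14.2.1. The pCR power stated there (80%) reproduces at 80.2% with an exact one-sided Fisher test at 0.1 and is not in question.

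**1. The terms side by side.**

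| Place | Term used | Role |
|---|---|---|
| Section 1 | locoregional control | hypothesis |
| Section 4.2 | locoregional control | objective |
| 14.5, opening sentence | locoregional control | listed endpoint |
| 14.5, time-to-event sentence | local recurrence | timed variable |

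The mismatch therefore lies within Section 14.5 as well as between 14.5 and the objective.

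**2. Expected nodal failures.** Assume that the cited TME-alone rate (1.6%) applies to Endo-HDR and the cited irradiated rate (1.3%) to control.

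- Endo-HDR: 92 × 0.016 = 1.5
- Control: 46 × 0.013 = 0.6
- Total: about 2.1
- Chance of no nodal failure in either arm: 0.984^92 × 0.987^46 = 0.227 × 0.548 = 0.12

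**3. Effect on the between-arm difference.** A local-only definition drops nodal failures from both arms, so the shift is the difference between the two nodal rates.

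- At the cited rates: 1.6 − 1.3 = 0.3 points.
- If the Endo-HDR nodal rate doubled to 3.2% (assumption): 3.2 − 1.3 = 1.9 points.
- For scale, take 5% local recurrence in each arm. Section 3.1 gives 5% at five years for the earlier Endo-HDR series; the control value is an assumption. As simple proportions, SE = √(0.05 × 0.95/92 + 0.05 × 0.95/46) = √(0.000516 + 0.001033) = 3.9 points.
- The shifts are thus 0.3/3.9 = 0.08 SE and 1.9/3.9 = 0.5 SE.

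**4. Could the nodal component be tested?** Exact one-sided Fisher test at 0.1, against 1.3% in control:

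| Assumed Endo-HDR nodal rate | Expected events of 92 | Power |
|---|---|---|
| 3.2% | 2.9 | 4% |
| 5% | 4.6 | 18% |
| 8% | 7.4 | 52% |

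**5. Share of one arm's events.** Adding nodal failure to 5% local recurrence as wholly separate events, the nodal share in the Endo-HDR arm is 1.6/6.6 = 24%, or 3.2/8.2 = 39% at the doubled rate. These are upper bounds at those nodal rates. Section 3.1 does not say that the 1.6% is isolated nodal failure, and any nodal failure accompanied by local failure would be counted anyway. Nor does it say that the 5% excluded nodal cases.

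**The case against.** The strongest reply is that the plan is silent on nodal failure and does not exclude it. That is fair in several respects.

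- Section 14.5 does not confine itself to local recurrence. Its opening sentence lists locoregional control, and the list "distant metastases free survival, progression free survival, and local recurrence" includes an outcome in which a nodal failure would ordinarily count. However, the events of progression free survival are also undefined, and pooling nodal with distant failure would not answer the locoregional objective.
- Section 3.1 reports one lateral pelvic nodal case within a series of 100 local recurrences after TME, so the term may be meant loosely. This weakens any claim that nodal failure is shut out, but it also shows why a definition is needed.
- Section 3.1 calls the nodal concern theoretical and argues that such failures are rare. Section 3.2.1 raises the localization of dose as a further concern. A reader might infer that nodal failure is the single harm the protocol has in view; the documents do not support that.
- A reader might also infer that the comparison is materially biased toward Endo-HDR, or take the 24% and 39% as the size of that bias. They describe one arm and are upper bounds. The between-arm shift at the cited rates is a small fraction of its standard error.

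It can also be said that changing one word would achieve little while the sentence still runs every outcome to death. That stands, and the end date has to be corrected together with the term.

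**Conclusion.** The point holds as a mismatch between objective and timed variable, with both terms undefined. Whether a pelvic nodal failure is an event is left to the reader of Section 14.5, on the component where the arms' treatment fields differ. It should be corrected, but it does not touch the primary pCR analysis.

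The expected numerical consequence is small, and the trial cannot settle the nodal question by a test whichever definition is used. The estimates assume that rates from a trial of short-course radiotherapy carry over to these two arms. They also ignore censoring. The 5% comes from a series in which node-positive patients also received postoperative external beam treatment, whereas Section 7.4.7 describes chemotherapy only, so it serves for scale and is not a forecast. The case for the change rests on measuring what the objective names.

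**What to change.** In Section 14.5, replace local recurrence with time from randomization to locoregional recurrence, and:

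1. Define the event by site: anastomosis, tumor bed or presacral space, mesorectum, or iliac, obturator, lateral pelvic or inguinal nodes.
2. Date the event at recurrence, not at death. Treat death without recurrence as a competing event and present cumulative incidence by arm.
3. Count a pelvic failure whether or not distant metastasis came first.
4. Report the local and pelvic nodal components separately by arm, using the annual CT already in the calendar.
5. Label the nodal component descriptive, giving the expected count of about 2 as the reason.

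The cost is SAP wording and one site-of-failure field on the case report form. No additional imaging is needed.
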